11.4 Exploratory Objectives Analysis

Refer to [section 8.1.3](#) of the protocol for the exploratory immunogenicity endpoints. A separate SAP will be issued specifically for the exploratory objective analysis.

12. EFFICACY ANALYSIS

Not Applicable.

13. SAFETY ANALYSIS

Refer to [section 8.1.1.1](#) of the protocol for the primary safety endpoints.

The safety assessments will include summaries of the following categories of data collected for each subject:

- Vaccine exposure.
- Solicited local and systemic adverse events.
- Unsolicited adverse events.
- Clinical laboratory parameters.

13.1 Analysis of Extent of Exposure

The frequencies and percentages of subjects with vaccination will be summarized overall and by vaccine group. Data will be tabulated for the All Enrolled Set.

13.1.1 Safety Completeness Analysis

Solicited adverse events

The safety completeness analysis on solicited adverse events aims to identify subjects who completed diary cards, irrespective of severity. The analysis will show the number of subjects with *valid data* by solicited adverse event and time point. *Valid data* in the context of the safety completeness analysis are all data entered in the diary card (including implausible values) except “Not done/unknown”.

Four summaries will be produced:

1. The frequencies of subjects who provide diary cards by dosage group.
2. For each solicited adverse event, the frequencies of subjects with *valid data* will be presented by dosage group and time point: 30 minutes post-vaccination and by day for Days 1 through 14.
3. For each type of solicited adverse event (local, systemic) and indicators of solicited adverse events, such as analgesic use, the frequencies of subjects with *valid data* by vaccine group, aggregated over time points: Days 1-14 (without 30 minutes).
4. For each solicited adverse event, the frequencies of subjects with *valid data* by vaccine group, aggregated over time points: Days 1-14 (without 30 minutes).

For the corresponding percentages, the denominator will be the respective numbers of exposed subjects, i.e., subjects who received a vaccination and were still in-study for that time point or time interval, irrespective of whether or not a diary card was present.

All analyses will be based on the ‘as treated’ analysis set.

13.2 Solicited Local and Systemic Adverse Events

For details, refer to [section 7.1.1](#) of the protocol.

Plausible observations are those with non-missing values other than those “Not done/unknown” or implausible values (see [section 6.3](#)). Implausible measurements will be excluded from summary tables but included in listings.

Solicited adverse events will be recorded at 30 minutes and Day 1 directly into the clinical database; and, from Day 2 to Day 14 in the subject diaries.

The analyses of solicited adverse events will be performed separately at these intervals: 30 minutes, Days 1-4 (without 30 minutes), Days 5-8, Days 8-14, Days 1-8 (without 30 minutes) and Days 1-14 (without 30 minutes). In addition, solicited AEs ongoing after day 14 will be presented as unsolicited AEs.

In the case of local AEs, for grades 1 to 3 (i.e., Mild to Severe), refer to Appendix A in the protocol. Grade 4 (Potentially Life Threatening) will be defined as follows (see also Appendix 2):

- Pain: Emergency room (ER) visit or hospitalization.
- Tenderness: ER visit or hospitalization.
- Erythema/Redness: Necrosis or exfoliative dermatitis.
- Induration/Swelling: Necrosis.

(Guidance for Industry Toxicity Grading Scale for Healthy Adult and Adolescent Volunteers Enrolled in Preventive Vaccine Clinical Trials, USDA, 2007).

All summary tables will include the number and percent of subjects with solicited adverse events by dosage group and time interval as well as overall.

Summary tables of solicited adverse events by severity and maximal severity will be created. Summary tables showing the occurrence of any local or systemic solicited adverse event will also be created.

The solicited local adverse events include these evaluations at the injection site: erythema, induration, swelling and pain. For erythema, induration and swelling recorded originally as diameters (mm), these categories will be used to summarize the data: None (0 mm), Grade 0 (<25 mm), Any (\geq 25 mm) with subcategories for Mild (25-50 mm), Moderate (51-100 mm) and Severe ($>$ 100 mm).

In the case of systemic AEs, for grades 1 to 3 (i.e., Mild to Severe), refer to Appendix B in the protocol. Grade 4 (Potentially Life Threatening) will be defined as follows (see also Appendix 3):

- Fever: >40 C (>104 F)
- Chills: ER visit or hospitalization
- Loss of Appetite: ER visit or hospitalization
- Nausea: ER visit or hospitalization for hypotensive shock
- Vomiting: ER visit or hospitalization for hypotensive shock
- Diarrhea: ER visit or hospitalization
- Generalized Myalgia: ER visit or hospitalization
- Generalized Arthralgia: ER visit or hospitalization
- Headache: ER visit or hospitalization,
- Fatigue: ER visit or hospitalization,
- Generalized Rash, ER visit or hospitalization Urticaria: ER visit or hospitalization.

Body temperature will be broken down by route of measurement according to the recommendations of the Brighton collaboration and will be summarized according to the 3 schemes described below:

- by 0.5 °C increments: <36.0 , ≥ 36.0 - <36.5 , ≥ 36.5 - <37.0 , ≥ 37.0 - <37.5 , ≥ 37.5 - <38.0 , ≥ 38.0 - <38.5 , ≥ 38.5 - <39.0 , ≥ 39.0 - <39.5 , ≥ 39.5 - <40.0 , ≥ 40.0 °C
- by 1.0 °C increments: <36.0 , ≥ 36.0 - <37.0 , ≥ 37.0 - <38.0 , ≥ 38.0 - <39.0 , ≥ 39.0 - <40 , ≥ 40 °C

- $<38.0, \geq 38.0$ °C

Fever, defined as a body temperature of ≥ 38 °C irrespective of route of measurement, will be considered a systemic adverse event.

The analyses will encompass summaries of the data on five levels:

1. Daily reports of subjects with solicited adverse events.
2. Time of first onset of solicited adverse events (excluding 30 min post-vaccination).
3. Solicited adverse events, maximum event severity by event and time interval.
4. Number of days with solicited adverse events.
5. Solicited adverse events and indicators of solicited adverse events, occurrence of at least one event by category (local, systemic) and time interval.

For each of the time intervals presented in the summaries, only subjects with at least one plausible observation for the solicited adverse events will be included.

Level 1: Daily reports of solicited adverse event

For each time interval, only subjects with at least one plausible observation for the solicited adverse event will be included in the analysis. For each time interval, the number and percent of subjects will be presented by dosage group, solicited adverse event and overall.

Level 2: Time of first onset of solicited adverse events

The **time of first onset** of a solicited adverse event experienced by each subject is the time point at which the event first occurred. For erythema, induration and swelling, a threshold of ≥ 25 mm will be used. The summary will provide the frequencies and percentages of subjects with first onset of each solicited adverse events by dosage group and time point.

For each dosage group, the first onset of the adverse event will be used for each subject.

Level 3: Solicited adverse events, maximum event severity by event and interval

The **maximum event severity** will be defined if there is at least one plausible observation within the time interval. Each subject's data will be aggregated across the time intervals and summarized according to the maximal severity observed for each adverse event,

followed by a summary across subjects for each dosage group. Subjects without any solicited adverse event data in the interval will be excluded from the analysis.

Level 4: Number of days with solicited adverse events

The number of days with the adverse event is defined irrespective of severity. This means at least ‘mild’ solicited adverse event that are assessed qualitatively and ≥ 25 mm for erythema, induration and swelling. If a solicited adverse event continues beyond day 14 the period after day 14 is added.

The frequency distribution of the number of days will be provided in a summary table by dosage group and adverse event.

Level 5: Solicited adverse events, occurrence of at least one event by category (local, systemic) and interval.

The **occurrence of at least one solicited adverse event** is defined as “any” for a subject who reports greater than “Grade 0” (≥ 25 mm for erythema, swelling and induration) for the respective event and “Grade 0” otherwise. The occurrence of at least one solicited adverse event (i.e., none versus any) will be summarized by category (i.e., local, systemic, any), by dosage group, and by time interval.

Medications to treat or prevent pain or fever will be summarized by frequencies and percentages of subjects reporting use of the medications by interval: 30 min, Days 1-4 (without 30 min), Days 5-8, Days 1-8 (without 30 min), Day 8-14, Days 1-14 (without 30 min).

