APPENDIX 2: GRADING SCALES FOR SOLICITED LOCAL ADVERSE EVENTS*

(Adapted from CBER 2007b)

Adverse event Following Administration of Injectable Product	Mild (Grade 1)	Moderate (Grade 2)	Severe (Grade 3)
Pain	present but does not interfere with activity	interferes with activity	prevents daily activity
Induration / Swelling / Erythema	25 – 50 mm	51 – 100 mm	> 100 mm

*Adapted from CBER 2007 to enable ease of reporting by Subjects in the source documents for 'patient reported' solicited adverse events. This toxicity grading scale is a Novartis standard that is used for patient reporting.

Grade 4 (Potentially life-threatening):

- Pain: Emergency room (ER) visit or hospitalization.
- Tenderness: ER visit or hospitalization.
- Erythema/Redness: Necrosis or exfoliative dermatitis.
- Induration/Swelling: Necrosis.

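### Grade 4 erythema, induration and swelling are defined without a size condition, but the solicited-reaction tables for these signs sort by diameter only and have no Grade 4 category

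*SAP*

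**What the plan says.** **Grade 4 definitions.** SAP Section 13.2 refers to the protocol for Grades 1 to 3 of the local reactions and defines Grade 4 itself. For erythema the entry is "Erythema/Redness: Necrosis or exfoliative dermatitis". For the other two signs, repeated in Appendix 2, it is "Induration/Swelling: Necrosis". Neither entry mentions a diameter.

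**Summary categories.** Later in Section 13.2, the sentence on these three signs reads "recorded originally as diameters (mm), these categories will be used to summarize the data: None (0 mm), Grade 0 (<25 mm"), followed by Any from 25 mm upward, "with subcategories for Mild (25-50 mm), Moderate (51-100 mm) and Severe" (above 100 mm). The list ends there.

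**Analysis levels in Section 13.2.**
- Level 2, first onset: "For erythema, induration and swelling, a threshold of" 25 mm or more applies.
- Level 3, maximum severity: subjects are summarised by the highest severity observed for each event. No diameter cut is given.
- Level 4, number of days: "This means at least ‘mild’ solicited adverse event that are assessed qualitatively and" 25 mm or more for the three measured signs.
- Level 5, occurrence: an event "is defined as “any” for a subject who reports greater than “Grade 0", with a parenthesis setting this at 25 mm or more for the three signs. Everything else is Grade 0.

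**The concern.** The plan defines its worst local grade by the nature of the lesion, then summarises the same signs by a measurement that does not carry that information. A small necrotic lesion meets the Grade 4 definition and also falls below the cut at which the sign is counted.

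Safety is a primary objective (Section 2.1). The Day 29 analysis serves to select an LHD153R dosage, and its safety tables to Day 29 are treated as final (Section 14.1). A per-sign table that shows a potentially life-threatening reaction as Grade 0, or as Mild or Moderate, would give a wrong picture of that sign in the affected dosage group.

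**Working it through.** The plan gives no figure to reproduce, so the check is to apply its rules literally to a lesion with necrosis.

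Inputs, all from SAP Section 13.2 (Grade 4 also in Appendix 2):
- Grade 4 if necrosis is present (for erythema, also if exfoliative dermatitis is present), whatever the size.
- Diameter categories: None 0 mm; Grade 0 below 25 mm; Mild 25-50 mm; Moderate 51-100 mm; Severe above 100 mm.
- Levels 2 and 4, and the Level 5 parenthesis: the sign counts from 25 mm.

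| Diameter of necrotic lesion | Grade by definition | Diameter category | Onset and days (Levels 2, 4) | Level 5, this sign |
|---|---|---|---|---|
| 5 mm | 4 | Grade 0 | none, zero | Grade 0 |
| 10 mm | 4 | Grade 0 | none, zero | Grade 0 |
| 24 mm | 4 | Grade 0 | none, zero | Grade 0 |
| 25 mm | 4 | Mild | counted | any |
| 60 mm | 4 | Moderate | counted | any |
| 120 mm | 4 | Severe | counted | any |

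The diameter category never agrees with the defined grade. Below 25 mm the sign is also lost from Levels 2, 4 and 5.

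Level 3 has to be read separately. It takes the highest severity observed and has no cut, so it could show Grade 4. The text does not say which grade applies when the Grade 4 finding and the diameter category disagree. The ordering Mild < Moderate < Severe in Section 8.7.3 stands under unsolicited events and does not settle the matter.

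Size: Table 1 gives 16 subjects in each LHD153R group, and 4 controls in each of 4 cohorts, 4 × 4 = 16. One misgraded subject is 1/16 = 0.0625, or 6.25% of the group. If the lesion is under 25 mm, the group's 'any' rate for that sign is too low by the same 6.25 percentage points.

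Scope: only erythema, induration and swelling are affected. Grade 4 pain and tenderness rest on an emergency room visit or hospitalisation and do not meet the diameter rule.

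**The case against.** The strongest reply is that the diameter list only bins a measured variable. It does not say that a lesion with identified necrosis must be graded by diameter. Section 13.2 defines four grades and then calls for tables by severity and maximal severity, so a programmer could naturally feed all four into Level 3. The Level 5 words "for a subject who reports greater than" Grade 0 would, taken alone, include Grade 4. The table shells are in a separate document and may carry a Grade 4 row.

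Part of this stands. Level 3 is silent rather than wrong. A reader might infer that every severity table hides Grade 4, but the text does not go that far. The reply does not rescue the rest. The category list is what the SAP prescribes for these signs and it has no Grade 4 entry. The Level 5 parenthesis fixes the threshold at 25 mm and assigns Grade 0 otherwise. Shells cannot change the derivation rules for Levels 2, 4 and 5.

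Two further readings are tempting and unsupported:
- *The subject would be recorded as having no local reaction.* Level 5 is summarised by category, and local events include pain. The subject counts as 'any local' through pain, or through another of the three signs at 25 mm or more. No rate for any local reaction follows from the misgrading of one sign.
- *The event would be invisible when a dosage is chosen.* Section 13.3 tabulates and lists serious events, medically attended events and events leading to withdrawal. Reactions ongoing after Day 14 are also presented as unsolicited events, and the DMC reviews safety data between stages (Section 15).

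**Conclusion.** The contradiction is real, and it is confined to the solicited-reaction tables. For erythema, induration and swelling, the stated categories and the rules for Levels 2, 4 and 5 do not implement the plan's own Grade 4 definition, and Level 3 does not say that Grade 4 overrides diameter. Below 25 mm a Grade 4 lesion is tabulated as Grade 0 for that sign. From 25 mm upward it is under-graded in the category table.

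Each such subject is 6.25% of a 16-subject group. That is the effect of a single hypothetical event: the SAP gives no expected rate, and nothing here says such an event is likely. The conclusion assumes that the rules are programmed as written and that necrosis or exfoliative dermatitis is recorded alongside the diameter. The point is worth correcting because it touches a primary safety output and the correction is small.

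**What to change.** Reconcile the passages in Section 13.2 by applying the SAP's existing Grade 4 definition:

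1. Add a Grade 4 (potentially life threatening) row under Any for erythema, induration and swelling.
2. State that in the severity and maximum-severity tables (Level 3) the Grade 4 criterion takes precedence over the diameter category.
3. In Levels 2, 4 and 5, read the threshold as 25 mm or more, or Grade 4.

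The cost is a few lines of SAP wording and derivation, plus one table row. This assumes that the necrosis or exfoliative dermatitis finding, which the Grade 4 definition already requires, is captured in the data. The SAP does not say how, so that should be confirmed first.

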13.3 Unsolicited Adverse Events

All the unsolicited adverse events occurring during the study, judged either as probably related, possibly related, or not related to vaccination by the investigator, will be recorded.

The original verbatim terms used by investigators to identify adverse events in the Case Report Forms (CRFs) will be mapped to preferred terms using the MedDRA dictionary. The unsolicited adverse events will then be grouped by MedDRA preferred terms into frequency tables according to system organ class. All reported adverse events, as well as adverse events judged by the investigator as at least possibly related to study vaccine, will be summarized by dosage group, according to system organ class and preferred term within system organ class. When an unsolicited adverse event occurs more than once for a subject, the maximal severity and strongest relationship to the dosage group will be counted.

Only treatment-emergent adverse events will be analyzed, i.e., excluding those after a subject has given informed consent but before vaccination. The selection of unsolicited adverse events and the assignment to time intervals (Days 1-14 after vaccination, and from Day 15 post vaccination until study termination) will be done by day of onset and not by days ongoing/persisting.

The analysis of unsolicited adverse events comprises the following categories:

- Any unsolicited adverse event.
- Possibly or probably related unsolicited adverse events.
- Unsolicited adverse events leading to death.
- Serious adverse events.
- Possibly or probably related serious adverse event.
- Unsolicited adverse events leading to premature withdrawal from study.
- Medically attended adverse events.
- Adverse events of special interest (AESI).
- New onset of chronic disease (NOCD).

Data listings of all adverse events will be provided by subject. In addition, adverse events in the categories above will be provided as listed data.

13.4 Combined Solicited and Unsolicited Adverse Events

A summary of subjects with all combined solicited (regardless of their duration) and unsolicited adverse events will be provided. Solicited adverse events will be coded by MedDRA. For clintrial.gov posting purposes, a summary of combined solicited and unsolicited non-serious adverse events will be produced. A further differentiation of combined adverse events according to seriousness, severity, or relationship is not possible.

13.5 Clinical Safety Laboratory Investigations

Baseline will be defined as the last non-missing assessment prior to vaccination.

Clinical safety laboratory values, and change-from-baseline values (baseline to 24 hours, to Day 8 and to Day 29), will be summarized (mean, standard deviation, median, minimum, and maximum) at each time-point of assessment, by dosage group, for the subset of subjects in the Safety Set with available laboratory data.

The frequencies of subjects with clinical laboratory values below, within, or above normal ranges will be tabulated for each clinical laboratory variable by dosage group and time-point of assessment (3 x 3 shift tables).

The percentages of subjects that show a ‘range change abnormal high’ (RCAH) or a ‘range change abnormal low’ (RCAL) are to be tabulated for each clinical laboratory variable by dosage group and time point of assessment. A RCAH is a laboratory value that is low or normal at baseline but high post-baseline. A RCAL is a laboratory value that is normal or high at baseline but low post-baseline.

Laboratory values will also be classified and tabulated according to Center for Biologics Evaluation, Research and Review (CBER) toxicity criteria ([CBER 2007b](#)). Refer to appendices C, D and E for the toxicity scales (grades 1 to 4) for laboratory abnormalities of the clinical chemistry, hematology and urine tests respectively.

Laboratory values that are outside the normal range will also be flagged in the data listings, along with corresponding normal ranges, toxicity grade, and assessment of clinical significance.

For subjects presenting at least one clinically significant value, an additional listing will be provided of all laboratory results by vaccine group, by subject, and by relevant parameter. Clinical significance assessed by the investigator will be presented.

13.6 Concomitant Medication

The frequencies and percentages of subjects reporting concomitant medications will be tabulated overall and by dosage group. Medications (generic drug name) will be coded using the WHODRUG dictionary ([section 8.7.5](#) defines prior and concomitant medications).

14. INTERIM ANALYSIS

14.1 Interim Analysis

A safety and immunogenicity interim analysis for the selection of an LHD153R adjuvant dosage will be performed based on the data collected through Day 29 from subjects enrolled in all cohorts. This analysis will be performed by personnel not involved in study decisions. The results will be unblinded at the group level thereby preserving the blind for individual subjects. No adjustment to the overall alpha will be performed as the data collected subsequent to this analysis involve secondary and exploratory endpoints.

The interim analysis is to be considered final with regards to the Immunogenicity and Safety Tables up to Day 29.

14.1.1 Futility Analysis

Not applicable.

15. DATA MONITORING COMMITTEES

An independent DMC will be implemented to review safety data during scheduled periodic reviews. The DMC will review safety data collected until Day 14, as described in the DMC charter, after enrollment of the first 5 subjects in each cohort, before proceeding with enrollment of the remaining 15 subjects in each cohort.

In addition, enrollment of the first 5 subjects of the next cohort will only proceed after the Day 14 safety results of the first 5 subjects of the previous cohort have been reviewed. Furthermore, all available Day 14 and Day 29 safety results will be included in DMC reviews between the different enrollment stages.

16. PEER REVIEW

Analyses/Outputs requiring statistical peer review correspond usually to the analyses of the primary and secondary objectives, and data conversion programs. Peer review of these analyses should be performed in accordance with the applicable procedures for validation of SAS programs used in clinical data analysis.

These analyses will be peer reviewed by a biostatistician independent from the study:

- Primary safety analysis.
- Primary immunogenicity analyses.
- Secondary immunogenicity analyses.
- Statistical models.

Programming will be validated by an independent programmer. Statistical models and populations employed will be checked by an independent biostatistician.

17. LIST OF FINAL REPORT TABLES, LISTINGS AND FIGURES

For the complete list of tables, listings and figures, please refer to the Table of Contents (TOC) stored in [Enterprise/eTMF Repository/V132_01EXP/Cluster Documents/Statistical analysis/Statistical analysis Plan.]

These names will be used in the tables and listings for the vaccine groups:

Vaccine Group	Table Column Titles
A	MenC
B	LHD153R 12.5
C	LHD153R 25
D	LHD153R 50
E	LHD153R 100

Columns headings can be split after the plus sign.

In all tables, listings and figures, vaccine groups will be labeled as “MenC”, “LHD153R 12.5”, “LHD153R 25.0”, “LHD153R 50.0” and “LHD153R 100.0”.

